6.2.2.2. Data Handling Rules

For ELISpot, values below the positivity threshold will be imputed with half of the threshold. For ICS, values below the LLOQ will be imputed with half of the LLOQ (LLOQ/2).

For the calculation of fold increases, ELISpot values below the positivity threshold will be imputed with the threshold; and ICS values below the LLOQ will be imputed with the LLOQ.

6.2.2.3. Analysis Methods

The cellular immune responses will be evaluated separately for each cohort of the study. Within each cohort, the data will be presented by vaccination schedule. The cellular data will not be presented by age stratum. See [Table 4](#) for details.

Summary statistics (ie, median, quartiles [Q1, Q3]) will be presented for all the continuous cellular immunogenicity outcomes (ie, ELISpot and ICS) at each time point. Also, the median fold increases (from Pre-dose 1, Pre-dose 2 and Pre-dose 3 [only for the Cohort 1 substudy]) with the corresponding quartiles (Q1 and Q3) will be presented per time point for these parameters.

Graphical representations (on a \log_{10} -scale) will be provided using dot plots, by vaccination schedule. Also, regimen profiles of the medians and the quartiles (Q1 and Q3) will be presented. Another regimen profile (medians and quartiles) will be generated by pre-existing antibody response against Ad26 vector (ie, pre-existing Ad26 versus no pre-existing Ad26). Responder and positive sample interpretation rates will be summarized (ie, showing number, percentage and the corresponding exact 95% Clopper-Pearson CIs) per timepoint. A data listing will also be generated.

For ICS, the proportions of EBOV GP-specific CD4+ and CD8+ T cells (ie, cells producing at least 1 of the 3 investigated cytokines) will also be tabulated per timepoint and shown in a pie chart. The magnitude of each cytokine subset will be shown in a bar chart. Both pie chart and bar chart will be restricted to responders.

6.3. Immunogenicity Against the Vector

6.3.1. Humoral Immune Responses

For immunogenicity against the Ad26 vector, a vector-specific reference value will be defined as the value closest but prior to the administration of the vector.

6.3.1.1. Parameters

Immune responses, as measured by the Ad26 VNA (IC₉₀ titers) will be analyzed. The following will also be defined for Ad26 VNA titers:

Sample interpretation: a sample will be considered positive, if the value is above the assay-specific LLOQ.

6.3.1.2. Data Handling Rules

For the outcome (ie, Ad26 VNA), values below the LLOQ will be imputed with half of the LLOQ (LLOQ/2).

6.3.1.3. Analysis Methods

The humoral immune responses (ie, immunogenicity against Ad26 vector) will be evaluated separately for each cohort ([Table 4](#)). Within each cohort, the data will be presented by vaccination schedule.

The geometric means and corresponding 95% CIs will be calculated. Positive sample interpretation will be summarized (ie, showing number, percentage and the exact 95% Clopper-Pearson CI). A data listing will also be generated.

7. SAFETY

The safety and tolerability data include the following:

- AEs collected from signing of the informed consent form (ICF) onwards until the 42-day post-last vaccination (excluding third vaccination) visit.
- AEs collected from the day of the third vaccination onwards until 28 days thereafter (note: events that started before the third vaccination but are still present at the time of third vaccination will also be recorded).
- Serious adverse events (SAEs) and immediate reportable events (IREs) from signing of the ICF onwards until the end of the study.
- Solicited local and systemic AEs (reactogenicity) recorded during the first 8 days (including the day of the vaccination) following each vaccination.

The safety and tolerability data will be summarized based on the full analysis set. The analysis will be based on the actual dose (ie, Dose 1, Dose 2 and Dose 3 for the first, second and third vaccination, respectively) that the subjects received. For example, if Dose 2 is not administered to a subject, then that subject will not be included in the analysis of AEs in the Post-dose 2 period. Focus will be on safety signals detected during the Post-dose 1, Post-dose 2 and Post-dose 3 periods, as well as the Regimen phase.

In general, safety data will be evaluated separately for each cohort. Within each cohort, the data will be presented by vaccination schedule.

7.1. Adverse Events

The analysis of AEs is based on the medical dictionary for regulatory activities (MedDRA) coded terms as provided in the clinical database. All reported AEs (solicited local, solicited systemic, and unsolicited) during the vaccination periods (Post-dose 1, Post-dose 2 and Post-dose 3) (ie, AEs following vaccination and AEs that have worsened since baseline) will be included in the analysis. Listings of AEs will include all reported AEs.

It is important to note that the AEs include any occurrence that is new in onset or aggravated in severity, toxicity grade or frequency from the baseline condition, or clinically relevant abnormal results of diagnostic procedures, including clinically relevant laboratory test abnormalities.

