## **11.1. Endpoints**

### **11.1.1. Primary Endpoints**

- Adverse events, collected until the 42-day post-last vaccination (excluding third vaccination) visit.
- Serious adverse events and IREs, collected from signing of the ICF onwards until the end of the study.
- Solicited local and systemic adverse events (reactogenicity), collected until 7 days after each study vaccine administration.

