#### **Adverse Events (Including Reactogenicity)**

The verbatim terms used in the CRF by investigators to report adverse events will be coded using the Medical Dictionary for Regulatory Activities (MedDRA). All reported adverse events after vaccination (solicited local, solicited systemic, and unsolicited) will be included in the analysis. For each adverse event, the number and percentage of subjects who experience at least one occurrence of the given event will be summarized by group. Summaries, listings, datasets and/or subject narratives may be provided as appropriate, for those subjects who die, discontinue study vaccinations due to an adverse event, or experience a severe or serious adverse event. The analysis for solicited adverse events will be done on those subjects in the Full Analysis set for whom reactogenicity assessments are available in the database. The analysis of unsolicited adverse events will be done based on the Full Analysis set.

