Regimen*	Post-dose 1	Date and time of Dose 1 administration	Minimum of: a) 23:59 on the date of last contact (for early study discontinuations) b) 23:59 on the date of relative Day 29 Post-dose 1 c) one minute prior to Dose 2 administration d) 23:59 on the date of database cut-off (in case of interim analysis)
Post-dose 1 FU		One minute after the end of the Post-dose 1 period	Minimum of: a) 23:59 on the date of last contact (for early study discontinuation or completion) b) one minute prior to Dose 2 administration c) 23:59 on the date of database cut-off (in case of interim analysis)
Regimen*	Post-dose 2	Date and time of Dose 2 administration	Minimum of: a) 23:59 on the date of last contact (for early study discontinuation or completion) b) 23:59 on the date of relative Day 29 Post-dose 2 c) 23:59 on the date of database cut-off (in case of interim analysis) Note: subjects who do not receive Dose 2 will not have a Post-dose 2 period.
Post-dose 2 FU		One minute after the end of the Post-dose 2 period	Minimum of: a) 23:59 on the date of database cut-off (in case of interim analysis) b) 23:59 on the date of last contact (for early study discontinuation or completion)
Regimen*	Post-dose 3	Date and time of Dose 3 administration	Minimum of: a) 23:59 on the date of last contact (for early study discontinuation or completion) b) 23:59 on the date of relative Day 29 Post-dose 3 c) 23:59 on the date of database cut-off (in case of interim analysis) Note: subjects who do not receive Dose 3 will not have a Post-dose 3 period.

Post-dose 3 FU		One minute after the end of the Post-dose 3 period	Minimum of: a) 23:59 on the date of database cut-off (in case of interim analysis) b) 23:59 on the date of last contact (for early study discontinuation or completion)
-------------------	--	--	---

Note 1: * Regimen period includes both the Post-dose 1, Post-dose 2 and Post-dose 3 periods.

Note 2: FU = follow-up.

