7.1.3. Analysis Methods

In general, the AEs following vaccination will be summarized (ie, tables of descriptive statistics) by vaccination schedule and presented per period/phase. Similar summary tables will also be provided pooled by vaccine (dose).

Furthermore, unsolicited AEs will be summarized (showing number and percentage) by System Organ Class (SOC) and Preferred Term (PT). Solicited AEs (recorded by day) will be converted into the analysis format of unsolicited AEs (recorded by event) as detailed in Attachment 2. These solicited AEs will be summarized by class (local, systemic) and Preferred Term. For solicited as well as unsolicited AEs, tables focusing on severity will be created. Focus will also be on the relationship (to the study vaccine) of the solicited systemic and unsolicited AEs.

The SAEs, AEs with fatal outcome, AEs leading to permanent discontinuation from study vaccination, Grade 3 AEs and IREs will also be listed. A table summarizing all those parameters will further be created and presented per analysis period and vaccination schedule. Summary tabulations by SOC and PT for each of the category of events (ie, SAEs, AEs with fatal outcome, AEs leading to permanent discontinuation from boost vaccination, Grade 3 AEs and immediate reportable events) will also be generated on the entire reporting period. Subject narratives will be generated for these events, except Grade 3 AEs. For Grade 3 AEs, the narratives will only be generated for those AEs that are considered related to study vaccination.

For the solicited local and systemic AEs, the duration and time to first onset of the events will also be summarized. If a subject experiences more than 1 occurrence of a solicited event, the maximum duration of the events will be used. The time to first onset is defined as:

$$[\text{date of first onset} - \text{reference date} + 1]$$

The reference date is the start date of each vaccination period (ie, Post-dose 1, Post-dose 2 or Post-dose 3). Duration and time to onset of AEs will be expressed in days.

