1. PERIOD ALLOCATION OF ADVERSE EVENTS

Solicited events will always be allocated to the Post-dose 1 or Post-dose 2 period, as appropriate.

Unsolicited AEs will be allocated to the different periods per the following rules:

Step 1: Allocation of unsolicited events to the periods/phases:

The AEs present in the database are allocated to periods/phases based on their start date/time. If the start date/time of an event falls between (or on) the start and stop date/time of a period/phase, the AE is attributed to that period/phase (ie, AEs following vaccination).

Incomplete dates (ie, time and/or day and/or month and/or year missing):

- 1) In case of partial start or stop dates, the events are allocated to the periods/phases using the available partial information on start and end date; no imputation will be done. If, for instance, for the AE start date only month and year are available, these data are compared to the month and year information of the periods/phases. This rule may lead to multiplication of the event because of its assignment to multiple periods/phases (see below example).
- 2) In case of a completely missing start date, the event will be allocated to the appropriate period/phase (eg, Post-dose 1 or Post-dose 2) and consequently the Regimen period; except if the end date of the AE falls before the start of the Post-dose 1 or Post-dose 2 period.
- 3) In case of a completely missing end date (ie, only for the calculation of duration):
 - In case the AE is flagged as ongoing the date is imputed by the cut-off date of the analysis for subjects still ongoing in the study, and by the end date of the last period/phase for subjects who discontinued or completed the trial.
 - In case the AE is not flagged as ongoing, the end date is considered as unknown, and the date will remain missing.

Examples:

Screening Phase: start date: 14JUN2016 - stop date: 28JUN2016

Post-dose 1 period: start date: 28JUN2016 - stop date: 19JUL2016

1) Adverse event: start date: JUN2016- stop date: 15JUL2016

As the start date only has information about month and year, only this information will be used from the periods/phases (ie, assuming any day of Jun is possible) and therefore the AE will be assigned to the Screening Phase as well as to the Post-dose 1 period.

2) Adverse event: start date: JUL2016- stop date 14JUL2016

As the AE starts after the Screening Phase and after the start of the Post-dose 1 period, it is only assigned to the Post-dose 1 period.

Remarks:

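### SAP 7.1 confines the all-AE analysis to 28 days after each dose, 7.1.3 suggests otherwise, and no specified table gives the any-AE count on the protocol's primary endpoint window

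*SAP*

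**What the plan says.** Protocol 11.1.1 gives the first primary endpoint as "Adverse events, collected until the 42-day post-last vaccination (excluding third vaccination) visit". Protocol 11.5 adds "All reported adverse events after vaccination (solicited local, solicited systemic, and unsolicited) will be included in the analysis" and sets no 28-day limit. SAP Section 7 repeats the 42-day collection window.

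SAP 7.1 then defines what enters the analysis: "All reported AEs (solicited local, solicited systemic, and unsolicited) during the vaccination periods (Post-dose 1, Post-dose 2 and Post-dose 3"). It contrasts this with the listings, which hold every reported AE. In SAP Table 2 the Post-dose 2 period ends no later than "23:59 on the date of relative Day 29 Post-dose 2", and Post-dose 1 has the matching limit or stops at Dose 2 if that is earlier. Later time belongs to separate FU phases. A note to the table says "Regimen period includes both the Post-dose 1, Post-dose 2 and Post-dose 3 periods".

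Two other places read more broadly. SAP 7.1.3 states "In general, the AEs following vaccination will be summarized (ie, tables of descriptive statistics) by vaccination schedule and presented per period/phase". SAP Attachment 1, Step 1, says that if an AE starts within a period or phase, "the AE is attributed to that period/phase (ie, AEs following vaccination"). Step 2 of the same attachment calls the FU phases non-active. SAP 7.1.3 also names a set of tables that "will also be generated on the entire reporting period", but only for serious AEs, fatal AEs, AEs that stop vaccination, Grade 3 AEs and immediate reportable events.

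SAP Section 3, on changes to the planned analysis, lists only the two redefined immunogenicity sets.

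**The concern.** The study's primary objective is safety, and the AE endpoint has a stated window. A reader of the clinical study report would expect the number and percentage of subjects with any AE on that window. The SAP does not specify it.

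The SAP also supports two different programs. One follows 7.1 and leaves FU-phase AEs to the listings. The other follows 7.1.3 and Attachment 1 and tabulates them by phase. The two give different tables for Grade 1-2 unsolicited AEs that start more than 28 days after a dose.

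The uncovered part of the window also grows with the prime-boost interval. Protocol Section 11 says the primary analysis is meant to help choose among the schedules.

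**Working it through.** **Inputs.** Boost day b = 29, 57, 85 and the 42-day visit on Day 71, 99, 127, with windows of ±3 days on each (Protocol Table 3). Period ends are from SAP Table 2. For subjects primed but not boosted, AE collection ends 42 days after the prime (Protocol 9.1.6).

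**Plan's own figure.** b + 42 = 29 + 42 = 71, 57 + 42 = 99, 85 + 42 = 127. This matches Protocol Table 3.

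**Days outside the 7.1 periods.** Each full period covers 29 calendar days, the dose day counting as Day 1.

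- Before boost: max(0, (b − 1) − 29)
- After boost: 43 − 29 = 14
- Total window: b + 42

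| Group | Before boost | After boost | Outside / total | Share | Covered |
|---|---|---|---|---|---|
| 1 | 0 | 14 (Days 58-71) | 14 / 71 | 19.7% | 57 |
| 2 | 27 (Days 30-56) | 14 (Days 86-99) | 41 / 99 | 41.4% | 58 |
| 3 | 55 (Days 30-84) | 14 (Days 114-127) | 69 / 127 | 54.3% | 58 |
| Primed only | n/a | 14 (Days 30-43) | 14 / 43 | 32.6% | 29 |

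**Visit windows.** Varying b by ±3 and the 42-day visit over relative Days 40-46 gives:

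- Group 1: 11-19 days outside, of a 65-77 day window (15.9-24.7%)
- Group 2: 35-47 days outside, of 93-105 (37.6-44.8%)
- Group 3: 63-75 days outside, of 121-133 (52.1-56.4%)

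**Can the endpoint count be rebuilt from the specified tables if FU phases are tabulated?**

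- The Regimen total leaves out both main-study FU phases and takes in Post-dose 3, which the primary endpoint excludes.
- One subject can have AEs in several periods. Period counts therefore only bound the number of subjects with any AE, between the largest single count and the sum. Attachment 1 also lets a partly dated AE be counted in more than one period.
- Post-dose 2 FU ends at last contact or data cut-off. It does not stop at the 42-day visit or at Dose 3, so its count covers a different window.
- The tables pooled by vaccine are described as similar summaries and set no new window.
- The whole-period tables cover only the five categories listed above.

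None of these yields the endpoint count.

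**Illustration only.** Assume onset is uniform over the window (the documents give no AE rate by day) and that a given Grade 1-2 unsolicited AE has a true whole-window incidence p of 0.5% or 1%. The chance of seeing at least one case is 1 − (1 − p)^n. On the 7.1 periods alone, p is scaled by 57/71, 58/99 or 58/127. With the planned active-arm numbers in Cohort 1:

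| Group (n) | p = 0.5% | p = 1% |
|---|---|---|
| 1 (220) | 66.8% → 58.7% | 89.0% → 83.0% |
| 2 (220) | 66.8% → 47.6% | 89.0% → 72.5% |
| 3 (110) | 42.4% → 22.2% | 66.9% → 39.6% |

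The unscaled figures agree with Protocol Table 9 (67%, 89%, 42%, 67%).

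**The case against.** The best defence is that the broad reading is the intended one. Table 2 gives the FU phases their own start and stop rules, Attachment 1 has rules for combining events across them, and Section 7 only says that focus will be on the Post-dose periods and Regimen. Focus is emphasis, not exclusion. The protocol leaves analysis details to the SAP, names no AE periods and tests no hypothesis, so choosing 28-day periods is not in itself a departure. A pooled table would also compare 71, 99 and 127 days of follow-up, whereas the 28-day tables compare nearly equal lengths.

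The size can be over-read too. Days are not events, and 55 of Group 3's 69 days are the wait for boost, with no scheduled visit between Day 15 and the boost in Cohort 1. Solicited AEs fall within 8 days of a dose, inside the periods. Attachment 1 moves an FU event into the active period when it overlaps or directly follows an active-period event with the same preferred term. Post-dose 3 affects only about 90 substudy subjects.

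Most of this stands and limits the severity. It does not remove the point. Section 7.1 as worded sets the analysed AEs against the listings of all AEs, which conflicts with Protocol 11.5. The broad reading cures that conflict but still does not produce a subject count on the endpoint window. If 28-day periods are to carry the primary safety analysis, Section 3 is where a reader would look for that statement.

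**Conclusion.** The SAP is wrong as written on this point and should be fixed. Followed literally, 7.1 removes non-serious Grade 1-2 unsolicited AEs from every summary table for 20%, 41% and 54% of the nominal endpoint window in Groups 1, 2 and 3, and for 33% in primed-only subjects, apart from those Attachment 1 folds into an active period. Followed broadly, those AEs appear by phase, but the any-AE count on the primary endpoint window is still missing.

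The percentages assume nominal visit days, take Dose 1 as the start of the post-vaccination window, and count days rather than events. Groups 1 and 2 exist in every cohort; Group 3 exists only in Cohort 1. Data collection and the whole-period tables for the more serious categories are unaffected, and all AEs are listed.

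**What to change.** 1. Reword SAP 7.1 to agree with 7.1.3: state that AEs starting in the Post-dose 1 FU and Post-dose 2 FU phases are tabulated.
2. Add one table per cohort of all unsolicited AEs by system organ class and preferred term, with an any-AE subject count, from Dose 1 through the 42-day visit after the last vaccination, excluding Dose 3. Show it by schedule and by active or placebo, with a footnote that nominal follow-up is 71, 99 and 127 days in Groups 1, 2 and 3.
3. Keep the 28-day period tables as the near-equal-length comparison between schedules.
4. Declare the 28-day periods in SAP Section 3.

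The cost is SAP wording and one extra AE table per cohort from data already collected. Study conduct and data collection do not change.

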7.1.1. Definitions

Solicited AEs are precisely defined events (local and systemic) that subjects are specifically asked about and which are noted by subjects in the diary. All other AEs are considered unsolicited. Refer to Section 9.3 and Section 12.1.1 of the CTP¹ for further details.

Solicited Local (Injection Site) Reactions

The analysis of local solicited AEs will include:

- Pain/Tenderness
- Erythema
- Induration/Swelling
- Itching

Solicited Systemic Adverse Events

The analysis of systemic solicited AEs will include:

- Fever (defined as body temperature of 38°C or higher)
- Headache
- Fatigue/Malaise
- Myalgia
- Nausea/Vomiting
- Arthralgia
- Chills

Serious Adverse Events

SAEs will be collected from signing of the ICF until the end of the study. An SAE based on the International Council for Harmonization (ICH) and the European Union (EU) Guidelines on Pharmacovigilance for Medicinal Products for Human Use is any untoward medical occurrence that at any dose:

- Results in death
- Is life-threatening (the subject was at risk of death at the time of the event. It does not refer to an event that hypothetically might have caused death if it were more severe.)
- Requires inpatient hospitalization or prolongation of existing hospitalization
- Results in persistent or significant disability/incapacity
- Is a congenital anomaly/birth defect
- Is a suspected transmission of any infectious agent via a medicinal product
- Is medically important*.

*Medical and scientific judgment should be exercised in deciding whether expedited reporting is also appropriate in other situations, such as important medical events that may not be immediately life-threatening or result in death or hospitalization but may jeopardize the subject or may require intervention to prevent one of the other outcomes listed in the definition above. These should usually be considered serious.

Immediate Reportable Events

The following list of neuroinflammatory disorders are categorized as IRE, and should be reported to the sponsor within 24 hours of becoming aware of the event using the IRE form. Relevant data from the IRE form will be captured in the clinical database.

- Cranial nerve disorders, including paralyses/paresis (eg, Bell's palsy)
- Optic neuritis
- Multiple sclerosis
- Transverse myelitis
- Guillain-Barré syndrome, including Miller Fisher syndrome, Bickerstaff's encephalitis and other variants
- Acute disseminated encephalomyelitis, including site specific variants: eg, non-infectious encephalitis, encephalomyelitis, myelitis, myeloradiculomyelitis
- Myasthenia gravis and Lambert-Eaton myasthenic syndrome
- Immune-mediated peripheral neuropathies and plexopathies (including chronic inflammatory demyelinating polyneuropathy, multifocal motor neuropathy and polyneuropathies associated with monoclonal gammopathy)
- Narcolepsy
- Isolated paresthesia of >7 days duration

Causality

The solicited local AEs will be considered as related to the study vaccine, by definition. The unsolicited and solicited systemic AEs will be considered as related to the use of the study vaccine if the attribution is possible, probable or very likely. An AE will be considered not related with the use of the study vaccine if the attribution is not related or doubtful. Refer to Section 12.1.2 of the CTP¹ for further details.

Severity Criteria

The severity of the AEs is classified by the investigator as mild, moderate or severe using the Division of Microbiology and Infectious Diseases (DMID) Toxicity Table for Use in Trials Enrolling Healthy Adults (Attachment 3). For the pediatric, the severity of AEs is classified using the DMID Pediatric Toxicity Tables for Children Greater Than 3 Months of Age (Attachment 4).

Solicited events that are graded less than mild, are not considered AEs. For some solicited events (eg, induration/swelling), the diameter and grading (as reported by the investigator [ie, functional

grade]) are collected in the electronic case report form (eCRF). The diameter will be used to derive the toxicity grading. The worst grade should be used when both the diameter derived grade and the investigator-reported grade are available. If either the diameter-derived or the investigator-reported grade is available, then this should be used.

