**12.1.3. Severity Criteria**

Adverse events and laboratory data will be coded for severity using the toxicity grading tables in [Attachment 2](#) and [Attachment 3](#). For adverse events not identified in the table, the following guidelines will apply:

Mild	Grade 1	Symptoms causing no or minimal interference with usual social and functional activities
Moderate	Grade 2	Symptoms causing greater than minimal interference with usual social and functional activities
Severe	Grade 3	Symptoms causing inability to perform usual social and functional activities

*Note: Only clinically significant abnormalities in laboratory data occurring from signing of the ICF onwards will be reported as adverse events and graded using the table above.*

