7.1.2. Data Handling Rules

Missing data will not be imputed. If the severity or relationship of AEs to the study vaccine could not be derived (ie, missing or unknown), it will be considered as unknown, for analysis purposes. Local solicited AEs will be considered as related with the use of the study vaccine, by definition.

Solicited events will always be allocated to the analysis period (Section 2.1). For analysis purpose, the AEs will be allocated to periods and/or phases as described in Attachment 1.

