AE1: start date: 20JUN2016- stop date: 10JUL2016

AE2: start date: 08JUL2016- stop date: 18JUL2016

AE1 will be attributed to the Screening Phase and AE2 to the Post-dose 1 period.

Example for the above Scenario 3

AE1: start date: 18JUL2016- stop date: 28JUL2016

AE2: start date: 28JUL2016- stop date: 08AUG2016

As AE1 starts in the active period (Post-dose 1) and overlaps with AE2 which starts in a non-active phase (Post-dose 1 FU), this AE is considered as a single AE in the AE analysis starting on 18JUL2016 and ending on 08AUG2016 and is attributed to the Post-dose 1 period.

2. TRANSFORMING ON-SITE ASSESSMENTS AND DIARIES OF SOLICITED ADVERSE EVENTS INTO AN ANALYSIS FORMAT

When creating the analysis dataset for solicited AEs, solicited AEs (recorded by day) need to be converted into the format of unsolicited AEs (recorded by event). All diary data will be considered, as well as any post-dose on-site assessment (scheduled as well as unscheduled) within (including the day of vaccination) 8 days after vaccination. For solicited local AEs for which a diameter is measured, the maximum of diameter derived grade and investigator severity (if available) will be used. The start date of the AE will be considered as the date of first occurrence of the solicited AE (both local and systemic). If on subsequent day(s), the same grade is reported, the last reported date is used as the end date of the AE. A new record is created in case the grade of the event changes. If there is a time gap of at least one day between two (or more) occurrences of the same type of the solicited AE, then the second (and/or next) occurrence will be considered as a new AE. In case no data is reported for a day, this is analyzed as no event reported. If the on-site assessment differs in grade or relatedness (if collected) with the corresponding diary data, only the highest grade and relatedness assessment indicating the highest relatedness to study vaccination per AE will be kept in the analysis database and used in the tables and listings. The following example shows how the solicited AE should be converted into a format of unsolicited AEs:

Data from the Subject Diary

Subject: 0001

Solicited systemic AE: Headache

	On-site Assessment	Diary Data							
		Day 1 01Jan16	Day 1 01Jan16	Day 2 02Jan16	Day 3 03Jan16	Day 4 04Jan16	Day 5 05Jan16	Day 6 06Jan16	Day 7 07Jan16
Solicited AE									
Grade	2	1	1	0	3	3	1	0	0
Relatedness	Doubtful	Probable							

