Nausea/vomiting	Minimal symptoms; caused minimal or no interference with work, school or self-care activities	Notable symptoms; required modification in activity or use of medications; did not result in loss of work or cancellation of social activities	Incapacitating symptoms; required bed rest and/or resulted in loss of work or cancellation of social activities
Diarrhea	Slight change in consistency and/or frequency of stools	Liquid stools	Liquid stools greater than 4x the amount or number normal for the child
Appetite	-	Decreased appetite	Appetite very decreased, no solid food taken
Abdominal Pain	Mild	Moderate; no treatment needed	Moderate; treatment needed
Constipation	Slight change in consistency/frequency of stool	Hard, dry stools with a change in frequency	Abdominal pain
Reactogenicity	Grade 1	Grade 2	Grade 3
Local reactions			
Pain/tenderness at injection site	Aware of symptoms but easily tolerated; does not interfere with activity; discomfort only to touch	Notable symptoms; required modification in activity or use of medications; discomfort with movement	Incapacitating symptoms; inability to do work or usual activities; significant discomfort at rest
Erythema/redness	< 10 mm	10-25 mm	26-50 mm
Induration/swelling	< 10 mm	10-25 mm	26-50 mm
Itching at the injection site	Infrequent, brief episode of scratching, easily distracted from scratching	Frequent, longer episodes of scratching, difficult to distract	Near constant scratching, or scratching during sleep; excoriation of skin
Edema	< 10 mm	10-25 mm	26-50 mm
Rash at the injection site	< 10 mm	10-25 mm	26-50 mm
Systemic reactions			
Allergic reaction	Pruritus without rash	Pruritic rash	Mild urticaria

Headache	Minimal symptoms; caused minimal or no interference with work, school or self-care activities	Notable symptoms; required modification in activity or use of medications; did not result in loss of work/school or cancellation of social activities	Incapacitating symptoms; required bed rest and/or resulted in loss of work/school or cancellation of social activities
Fatigue/malaise	Minimal symptoms; caused minimal or no interference with work, school or self-care activities	Notable symptoms; required modification in activity or use of medications; did not result in loss of work/school or cancellation of social activities	Incapacitating symptoms; required bed rest and/or resulted in loss of work/school or cancellation of social activities

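### Pediatric Grade 3 for erythema and swelling stops at 50 mm, so a larger reaction gets no diameter-derived grade and its severity can be understated

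*SAP*

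**What the plan says.** SAP 7.1.1 (Severity Criteria) covers solicited local events for which a diameter is recorded, and gives induration/swelling as its example: "The diameter will be used to derive the toxicity grading". Where a diameter-derived grade and an investigator grade both exist, the worse one counts. SAP Attachment 2 repeats this: "the maximum of diameter derived grade and investigator severity (if available) will be used". Where only one exists, 7.1.1 says: "If either the diameter-derived or the investigator-reported grade is available, then this should be used". Where severity "could not be derived (ie, missing or unknown), it will be considered as unknown" (SAP 7.1.2), and nothing is imputed.

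For pediatric subjects 7.1.1 points to SAP Attachment 4. Its two relevant rows read "Erythema/redness < 10 mm 10-25 mm 26-50 mm" and "Induration/swelling < 10 mm 10-25 mm 26-50 mm", the three ranges being Grades 1, 2 and 3. Protocol Attachment 3 has the same ranges. Nothing in either table covers a diameter above 50 mm.

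**The concern.** A severity scale should not lose its grade at the severe end. The adult table (SAP Attachment 3) avoids this, because Grade 3 for both reactions is anything over 10 cm. The pediatric table does not, so the largest reactions in children are the ones without a derived grade.

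Solicited local events are part of a primary endpoint (protocol 11.1.1). SAP 7.1.3 plans severity tables, a Grade 3 listing, and narratives for Grade 3 events considered related to vaccination. SAP 7.1.1 treats every solicited local event as related by definition. A reaction above 50 mm that loses its derived grade can therefore drop out of all three outputs. The effect runs only towards understating severity.

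**Working it through.** No sample size, power or confidence limit in the plan depends on this rule, so there is no stated figure to reproduce. The check is to apply the rule as written.

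**Inputs**
- Derived grade, SAP Attachment 4: below 10 mm = 1; 10-25 mm = 2; 26-50 mm = 3; above 50 mm = none.
- Reported grade, SAP 7.1.1, 7.1.2 and Attachment 2: maximum of derived and investigator grade; if only one exists, that one; if neither, unknown.

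**Result**

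| Diameter (mm) | Derived grade | Investigator grade missing | Investigator 1 | Investigator 2 | Investigator 3 |
|---|---|---|---|---|---|
| 25 | 2 | 2 | 2 | 2 | 3 |
| 26 | 3 | 3 | 3 | 3 | 3 |
| 50 | 3 | 3 | 3 | 3 | 3 |
| 51 | none | unknown | 1 | 2 | 3 |
| 60 | none | unknown | 1 | 2 | 3 |
| 150 | none | unknown | 1 | 2 | 3 |

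From 26 to 50 mm the reported grade is 3 whatever the investigator wrote. At 51 mm and above it is whatever the investigator wrote, or unknown. With investigator grade 1, moving from 50 mm to 51 mm takes the reported grade from 3 to 1.

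**Does another rule close the gap?**
- SAP 7.2.1 moves a value lying between two grades to the worse neighbouring grade. It is confined to laboratory results, and a diameter above the top grade does not lie between two grades.
- The maximum-of-two rule gives no protection when one of the two grades does not exist.

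**How the SAP treated the same problem elsewhere.** The protocol's pediatric laboratory table has closed Grade 3 ranges. The SAP opened them: AST went from 3.0-8.0 x ULN in protocol Attachment 3 to ≥3.0 x ULN in SAP Attachment 4, and platelets from 25,000-49,999 to ≤49,999/mm³. The local-reaction rows of the same attachment were left closed, which looks like an oversight.

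**Who is graded under the rule.** Cohort 3 has 132 planned children (110 active) and two doses: 132 x 2 = 264 planned injections, placebo included. Cohort 2b has the same numbers. If both cohorts use Attachment 4, the totals are 132 + 132 = 264 children, 110 + 110 = 220 active, and 264 x 2 = 528 injections.

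**With Grade 3 set at ≥26 mm.** Every diameter above 50 mm gives Grade 3 in all four investigator columns. Nothing changes at 50 mm or below.

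**The case against.** The best defence is that investigators will supply the right grade. SAP 7.1.1 has them classify severity with the same pediatric table, whose erythema and swelling rows are purely by size. Someone grading a 60 mm reaction would naturally choose the top grade, and Grade 3 would be reported. That stands as a limit on the consequence: a mild or unknown grade is possible, not inevitable. It does not remove the defect. The SAP uses the diameter so that the reported grade cannot fall below what the measurement implies, and that safeguard is absent above 50 mm.

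Several stronger readings are tempting, and the documents do not support them:
- A reader might infer that protocol 12.1.3 sends a large painless reaction to mild. Its functional scale is introduced with "For adverse events not identified in the table, the following guidelines will apply", and erythema and swelling are identified in the pediatric table. The scale also grades interference with activities, not pain.
- A reader might infer that the lowest range turns a recorded 0 mm into a Grade 1 event. SAP 7.1.1 excludes solicited events below mild from the adverse events, and subjects are asked to note occurrences.
- A reader might take 528 as the number of affected events. It counts planned injections under the rule, placebo included.
- A reader might infer an effect on the pausing rules. In protocol 9.3.2 the solicited-reaction criterion names systemic reactions, while a remark in SAP Attachment 2 also mentions injection-site reactions. Those passages need reconciling with each other, but no pausing consequence is claimed here.

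The objection on scope also stands in part. The SAP does not say by name which cohorts are graded on Attachment 4, and the heading of its unit-conversion table refers to children under 12. The protocol treats anyone under 18 as pediatric (1.2.4) and lists ages 12-17 under the pediatric inclusion criteria (4.1.3), so Cohort 2b is probably covered, but not explicitly.

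**Conclusion.** The point holds as a specification defect in the severity grading of a primary safety endpoint. Above 50 mm the pediatric table yields no derived grade, and the reported grade can fall as the reaction grows. The possible error is an understatement of Grade 3 erythema and swelling in the severity tables, the Grade 3 listing and the narratives. The event itself is still counted as a solicited adverse event.

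The gap applies to Cohort 3 on any reading. It applies to Cohort 2b on the assumption that the protocol's definition of pediatric decides the table. If Cohort 2b is graded on the adult table, it has no gap at the top. The number of misgraded reactions cannot be computed, because the documents give neither the frequency of reactions above 50 mm nor how investigators would grade them. A flat statement that Grade 3 rates in children are biased downward would go further than the documents allow.

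**What to change.** In SAP Attachment 4, change Grade 3 for erythema/redness and for induration/swelling from 26-50 mm to ≥26 mm, in line with the pediatric laboratory rows. State in SAP 7.1.1 which cohorts are graded on Attachment 4 and which on Attachment 3.

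The edema and injection-site rash rows are also closed at 50 mm, but neither is among the solicited local events that SAP 7.1.1 analyses, so they need not be part of this change. No protocol amendment is needed: the derived grade is an analysis step, and the SAP has already departed from the protocol's pediatric laboratory ranges in the same way.

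The cost is two table cells and one sentence. Grade 3 local-reaction counts in children may rise slightly; nothing at 50 mm or below changes.
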